**Job Notes:**

This is the first revision (Version 2.0) of the Statistical Analysis Plan for this study. This version of the Statistical Analysis Plan is based on Version 2.0 of the study protocol.

## **Executive Summary:**

### Key Objectives:

The overall objective is to demonstrate noninferiority of multifocal (MF) contact lenses versus progressive addition lens spectacles (PALs) in the transition time [REDACTED] in presbyopes.

### Decision Criteria for Study Success:

Success of this study will be based on demonstration of noninferiority in transition time between distance and intermediate vision with MF contact lenses when compared to PALs, using a margin of 0.5.

# 1 Study Objectives and Design

## 1.1 Study Objectives

### PRIMARY OBJECTIVE

The primary objective is to demonstrate noninferiority in transition time between distance and intermediate vision with MF contact lenses compared to PALs.

[REDACTED]

[REDACTED]

[REDACTED]

[REDACTED]

[REDACTED]

## 1.2 Study Description

Key components of the study are summarized in Table 1-1.

[figure not shown]
Table 1-1 Study Description Summary

Study Design	Prospective, randomized, parallel group, double-masked for contact lens wearers, single-masked (investigator to type of brand) for PALs wearers
Study Population	Presbyopic subjects aged $\geq 38$ and $\leq 58$ years with normal eyes (other than correction for refractive error), whose habitual correction is either any MF contact lens (with a preference for Alcon Precision Profile Design wearers) with a LO or MED ADD (or equivalent to an ADD of max +2.00 D) or progressive addition lens spectacles. Wear of habitual correction must be at least 5 days per week and at least 6 hours per day.  Target to complete: 48 (12 per group) Planned to enroll: ~60
Number of Sites	2 (1 UK, 1 US)
Test Product(s)	
 
• AIR OPTIX® plus HydraGlyde® (Iotrafilcon B) Multifocal contact lens (AOHG MF)
 
• DAILIES TOTAL1® (delefilcon A) Multifocal contact lens
 

	(DT1 MF) 
 
DAILIES® AquaComfort Plus® (nelfilcon A) Multifocal contact lens (DACP MF)
 

Control Product(s)	Progressive addition lens spectacles (PALs)
Duration of Treatment	Test product(s): Up to 3 hours Control product(s): Up to 3 hours
Visits	Visit 1 – Screening Visit 2 – Exposure/Exit [0 - 14 days from Visit 1] *  *Randomization for subjects in the contact lens group will occur at Visit 2

A study design schematic is depicted in Figure 1-1.

**Figure Error! No text of specified style in document.–1 Study Design**

### 1.3 Randomization

A member of the Randomization Programming group at Alcon who is not part of the study team will generate the randomized allocation schedule(s) for study lens assignment.

Randomization will be implemented in Medidata Rave RTSM.

Qualifying subjects in the contact lens group will be randomized in a 1:1:1 ratio to one of 3 parallel groups to receive either AOHG MF, DT1 MF, or DACP MF, respectively. Habitual PALs wearing subjects will not be randomized.

## **1.4 Masking**

This study is double-masked for contact lens group and single-masked for PALs group (investigators will be masked to type and brand of PAL).

## **1.5 Interim Analysis**

There are no plans to conduct an interim analysis and no criteria by which the study would be terminated early based upon statistical determination.

## **2 Analysis Sets**

### **2.1 Safety Analysis Set**

Safety analyses will be conducted using the safety analysis set on a treatment-emergent basis. As such, the safety analysis set will include all subjects/eyes exposed to any study product evaluated in this study, except for the lenses used at Visit 2 for the purpose of parameter optimization and fitting as they are not intended for the assessment of safety. For treatment-emergent safety analyses, subjects/eyes will be categorized under the actual study product exposed.

Adverse events occurring from the time of informed consent but prior to first exposure to study products will be summarized in subject listings.

### **2.2 Full Analysis Set**

The full analysis set (FAS) is the set of all subjects assigned to PALs or randomized to the contact lens group who are exposed to any study product evaluated in this study, except for the lenses used for optimization and fitting.

### **2.3 Per Protocol Analysis Set**

The per protocol (PP) analysis set is a subset of FAS and excludes all data/subjects which have met any of the critical deviation or evaluability criteria identified in the Deviations and Evaluability Plan (DEP).

### 3 Subject Characteristics and Study Conduct Summaries

The following tables will be presented:

- Subject Disposition
- Analysis Sets
- Subject Accounting
- Demographic Characteristics
- Baseline Characteristics [REDACTED]

[REDACTED]

Demographic characteristics and subject accounting tables will be summarized on the safety, full, and per protocol analysis datasets. Baseline characteristics will be summarized on the full and per protocol analysis datasets.

In addition, the following subject listings will be provided:

- Listing of Subjects Excluded from Protocol Defined Analysis Sets
- Listing of Lens Assignment by Investigator
- Listing of Subjects Discontinued from Study

### 4 Effectiveness Analysis Strategy

This study defines 1 primary, [REDACTED]  
[REDACTED] All effectiveness evaluations will use the FAS as the primary analysis set.  
[REDACTED] analyses of the primary [REDACTED] will be conducted using the PP Analysis Set only if the number of subjects excluded from the PP Analysis Set exceeds 5% of the FAS.

Continuous variables will be summarized using the number of observations, mean, standard deviation, median, minimum and maximum, as well as confidence intervals/limits as applicable. Categorical variables will be summarized with counts and percentages from each category.

All data obtained in evaluable subjects/eyes will be included in the analysis. No imputation for missing values will be carried out for the primary [REDACTED]  
[REDACTED]

For all planned inferential analyses, alternative models/methods may be considered, for instance, if convergence cannot be achieved.

## 4.1 Effectiveness Endpoints

### Primary Endpoint

The primary endpoint is the average transition time, calculated from all (maximum of 3) voice recorded readings, recorded in seconds, during alternate viewing from distance (4 m) to intermediate (80 cm) and vice versa.

[REDACTED]

[REDACTED]

[REDACTED]

- | [REDACTED]
- | [REDACTED]
- | [REDACTED]
- | [REDACTED]
  - | [REDACTED]
  - | [REDACTED]
  - | [REDACTED]

- | [REDACTED]
  - [REDACTED]
- | [REDACTED]
- | [REDACTED]
- | [REDACTED]

## 4.2 Effectiveness Hypotheses

### Primary Effectiveness

The null and alternative hypotheses for the primary analysis are formulated in terms of the predefined margin of 0.5 for noninferiority:

$$H_0: \mu_{(MF)} - \mu_{(PAL)} \geq 0.5$$

$$H_a: \mu_{(MF)} - \mu_{(PAL)} < 0.5$$

where  $\mu_{(MF)}$  and  $\mu_{(PAL)}$  denote the mean of average transition time between distance and intermediate viewing for MF contact lenses and PALs, respectively.

[Redacted]

[Redacted]

[Redacted]

[Redacted]

[Redacted]

[Redacted]

[Redacted]

[REDACTED]

[REDACTED]

[REDACTED]

[REDACTED]

[REDACTED]

### 4.3 Statistical Methods for Effectiveness Analyses

#### 4.3.1 Primary Effectiveness Analyses

A mixed effect repeated measures model will be utilized to test these hypotheses, with a term for treatment (4 levels: AOHG MF, DT1 MF, DACP MF, and PAL). Within-subject correlation due to multiple observations per subject will be accounted for. Difference between MF (pooling all 3 MF groups) and PAL and the corresponding one-sided 95% upper confidence limit (UCL) will be computed. Noninferiority in transition time will be declared if the UCL is less than 0.5. Furthermore, if noninferiority is demonstrated, subsequent superiority will be tested and declared if UCL is less than 0. Otherwise, no further testing will be carried out on this endpoint.

Analysis of the mixed effect repeated measures model will be implemented in SAS. The pseudocode is provided below.

```
proc sort data = studydata;  
  by subject;  
run;
```

```
proc mixed data = studydata;  
  class subject lens;  
  model transitiontime = lens;  
  random subject;  
  repeated / subj = subject type = cs;
```

```
lsmeans lens;  
contrast 'Compare MF vs PALs' lens 1 1 1 -3;  
run;
```

Additionally, descriptive statistics will also be provided summarize:

- Average transition time for each individual MF lens group
- Average transition time for distance to intermediate viewing
- Average transition time for intermediate to distance viewing

[REDACTED]

[REDACTED]

[Redacted]

[Redacted]

[Redacted]

[Redacted]

[Redacted]

[Redacted]

[Redacted]

[Redacted]

[Redacted]

[Redacted]

[Redacted]

[Redacted]

[Redacted]

[Redacted]

[REDACTED]

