## 12.4 Effectiveness Analyses

This study	defines 1 primary,			
	All effectiveness evaluations will use the FAS as the primary analysis set.			
	analyses of the primary	will be		
conducted using the PP Analysis Set only if the number of subjects excluded from the PP				
Analysis S	Set exceeds 5% of the FAS.			

A sequential gatekeeping strategy will be used to control testing of multiple effectiveness endpoints. Therefore, the overall Type I error will be maintained at one-sided 0.05 with the following testing order:

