## 12.4.1.2 Analysis Methods

A generalized linear model will be utilized to test these hypotheses, with a term for treatment (4 levels: AOHG MF, DT1 MF, DACP MF, and PAL). Difference between MF (pooling all 3 MF groups) and PAL and the corresponding one-sided 95% upper confidence limit (UCL) will be computed. Noninferiority in transition time will be declared if the UCL is less than 0.5. Furthermore, subsequent superiority will be declared if UCL is less than 0.

19-Oct-2018 Protocol - Clinical

2.0; Most-Recent; Effective; CURRENT TDOC-0055656 Page 52 of 59

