## 12.8 Sample Size Justification

Sample size calculation is based on published results regarding response time for distance and near visual acuity, with high and low contrast.

To demonstrate noninferiority (margin = 0.5 seconds) as a one-tailed hypothesis with  $\alpha = 0.05$ , and using a common standard deviation of 0.456, 80% power can be attained with a sample size of 48 (12 per group). For a comparison using a 3:1 ratio, required sample sizes for 80% power are 24:8 (test:control).

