## 7 Sample Size and Power Calculations

Sample size calculation is based on published results regarding response time for distance and near visual acuity, with high and low contrast.

To demonstrate noninferiority (margin = 0.5 seconds) as a one-tailed hypothesis with  $\alpha = 0.05$ , and using a common standard deviation of 0.456, 80% power can be attained with a sample size of 48 (12 per group). For a comparison using a 3:1 ratio, required sample sizes for 80% power are 24:8 (test:control).

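### The protocol and the SAP prescribe different primary models and the SAP leaves its analysis row undefined, so the upper limit that decides noninferiority is not uniquely fixed

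*SAP*

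**What the plan says.** Protocol 12.4.1.2: "A generalized linear model will be utilized to test these hypotheses". The only term named is treatment, with four levels. Protocol 12.4.1 defines the endpoint as an average of at most three readings, and 12.4.1.1 defines each group mean as the mean of that average.

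SAP 4.3.1, for the same hypotheses: "A mixed effect repeated measures model will be utilized to test these hypotheses". It adds that correlation among repeated observations on a subject will be accounted for. Its pseudocode has both a random subject effect and a compound-symmetry repeated statement for the same subject. SAP 4.1 nevertheless keeps the averaged endpoint: "The primary endpoint is the average transition time, calculated from all (maximum of 3) voice recorded readings". SAP 4.2 keeps the group means as means of that average.

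The two texts are meant to be in step. The SAP's Job Notes state: "This version of the Statistical Analysis Plan is based on Version 2.0 of the study protocol". Both documents apply one rule: the one-sided 95% upper confidence limit for pooled MF minus PAL must lie below 0.5 for noninferiority and below 0 for superiority.

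**The concern.** One upper limit decides the trial, and two procedures are prespecified to produce it. An averaged endpoint gives one row per subject and leaves no within-subject correlation to model. The SAP's model needs several rows per subject, but its text does not say whether a row is a reading or a viewing direction.

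The two procedures also weight subjects differently. A model on subject averages counts each subject in a group equally. A mixed model on readings gives less weight to a subject with fewer readings. Fewer than three are allowed, and neither document imputes missing values. SAP section 4 also permits alternative models, for instance if convergence fails, so the choice of primary analysis could still be open once results are visible.

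**Working it through.** **Inputs from the documents.** Margin 0.5 s, one-sided alpha 0.05, SD 0.456, 12 per group, so 36:12 for pooled MF against PAL (protocol 12.8, SAP 7).

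**Assumed, because the documents give no figure.** 0.456 is the SD of a three-reading average. The intraclass correlation (ICC) of readings is 0.3 to 0.8. Rows are readings. The number of readings per subject varies as shown below.

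**1. The plan's own figure.** With a true difference of 0, the normal formula at 1:1 gives (1.645 + 0.842)² × 2 × 0.456² / 0.5² = 10.3, so 11 per group. The t test gives 79.9% power at 11 and 83.1% at 12 per group. At 3:1 it gives 78.9% for 21:7 and 83.6% for 24:8. Both stated sizes reproduce.

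**2. The planned comparison.** SE = 0.456 × √(1/36 + 1/12) = 0.152 s. With 44 df, t = 1.680 and the half-width is 0.255 s. Power at a true difference of 0 is about 94%, so the model conflict does not threaten power.

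**3. Three readings in every subject.** Estimate and SE are the same in both models, and the limits differ by 0.0000 s at the same df. If the mixed model used 144 − 48 = 96 df (an assumed software default; neither document states the method), t = 1.661 and the limit moves by (1.680 − 1.661) × 0.152 ≈ 0.003 s.

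**4. Why unequal counts matter.** The mixed model weights a subject with n readings by 1/[ICC + (1 − ICC)/n]. Relative to a subject with three readings, a subject with one has weight r = ICC + (1 − ICC)/3, which is 0.53, 0.67 and 0.87 at ICC 0.3, 0.5 and 0.8.

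**5. Readings lost at random.** Simulated trials compared the subject-average model with a restricted maximum likelihood compound-symmetry model, both with 44 df:

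| Subjects with 1 / 2 / 3 readings | ICC | Mean difference in limit at true 0.25 s | Decisions changed, true 0 | Decisions changed, true 0.25 s |
|---|---|---|---|---|
| 5 / 10 / 85% | 0.3, 0.5, 0.7 | 0.019, 0.011, 0.006 s | 1.8, 1.3, 0.3% | 5.7, 2.8, 1.0% |
| 15 / 25 / 60% | 0.3, 0.5, 0.7 | 0.030, 0.017, 0.010 s | 3.0, 1.8, 0.7% | 8.0, 5.3, 3.2% |
| 20 / 20 / 60% | 0.3, 0.5, 0.8 | 0.033, 0.021, 0.007 s | 4.0, 2.7, 0.5% | 7.5, 5.2, 1.8% |

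At a true difference of 0.5 s, in the first two patterns, both models declared noninferiority in about 4% to 7% of trials. Random loss therefore gives no clear sign of excess error in either.

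**6. Readings lost by slow subjects.** Suppose the slowest third of an arm, by underlying subject mean, keep one reading each. For a normal distribution that third averages 1.091 between-subject SDs above the mean. With b = 1.091 × between-subject SD, the weighted arm mean falls by b(1 − r)/(2 + r). The between-subject SD is 0.456 × √(ICC/r), which is 0.342, 0.395 and 0.438 s.

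- ICC 0.3: b = 0.373; 0.373 × 0.467/2.533 = 0.069 s
- ICC 0.5: b = 0.431; 0.431 × 0.333/2.667 = 0.054 s
- ICC 0.8: b = 0.478; 0.478 × 0.133/2.867 = 0.022 s

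Simulation agrees with these shifts. The sign depends on the arm:

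| Arm losing readings | Shift in MF minus PAL, ICC 0.3 / 0.5 / 0.8 | Mixed model: noninferiority declared at true 0.5 s |
|---|---|---|
| MF only | −0.07 / −0.05 / −0.02 s | about 13–14 / 11–12 / 7% |
| Both alike | about 0 | 5.9 / 6.4 / 5.2% |
| PAL only | +0.07 / +0.05 / +0.02 s | 1.7 / 2.6 / 2.9% |

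The subject-average model gave 4% to 5% with MF-only loss and with loss in both arms.

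**The case against.** The best defence is that this is a mismatch of labels with little numerical effect. Transition time is measured at one visit, nothing in the documents predicts many missing readings, and with complete data the mixed model estimates exactly the mean of the subject averages. If the rows are the two viewing directions, the reading-count calculations do not describe the SAP's model at all. Protocol section 12 also provides for analysis changes to be recorded in an amendment or the study report. The SAP's revision history is blacked out, so the lack of a visible reason for the change proves nothing.

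Most of this stands and limits the size of the point. It does not remove it. Recording a deviation afterwards does not fix the rule in advance, and doubt about what a row is forms part of the defect.

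Two stronger readings are tempting and unsupported. A reader might infer that the SAP's model favours noninferiority in general. It does so only if slow MF subjects lose readings and PAL subjects do not. Nothing in the documents points to that pattern, and the reverse pattern pushes the other way. A reader might also infer that readings will be analysed as if independent, with inflated error. Neither document specifies that: the protocol pairs its model with a per-subject average, and the SAP says that it allows for within-subject correlation.

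**Conclusion.** The contradiction is real and lies in current text. Two models are prespecified for one decision, and the SAP's model does not fit the endpoint as the SAP defines it unless a row is specified.

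If rows are readings, the limits coincide with three readings per subject and equal df. With 40% of subjects short at random, they differ by about 0.01 to 0.03 s on average, against a 0.5 s margin. Across the settings with 15% to 40% short, the decision changes in about 0.3% to 4% of trials at a true difference of 0 and 1% to 8% at 0.25 s. Loss that depends on slowness and differs between arms can move the mixed-model estimate by up to about 0.07 s in either direction. Loss that is alike in both arms moves it by about zero.

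These sizes rest on the assumed ICC, reading counts and meaning of the SD. This is a point to settle before database lock. It is not a threat to the trial's power or design.

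**What to change.** Name one primary analysis in both documents. The choice that matches the endpoint as defined is to compute one average per subject, fit a linear model with lens (four levels), and take the pooled MF minus PAL estimate (coefficients 1/3, 1/3, 1/3, −1) and its one-sided 95% upper limit from that model. In protocol 12.4.1.2, state a normal distribution and identity link. In the SAP pseudocode, request the estimate and its limit; the present contrast statement returns only a test.

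Keep any reading-level mixed model as supportive. Define its row and its df method, and use either the random subject effect or the compound-symmetry structure. With both, the two variance components for the same subject cannot be separated.

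The cost is a SAP wording change and one clarifying line in the protocol before database lock, with no new data. The statistical price is a small loss of precision if readings are missing completely at random.

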#### 5 INTRODUCTION

#### 5.1 Rationale and Background

Presbyopia is an age-related vision condition in which the crystalline lens gradually loses its ability to change shape when acted upon by the ciliary muscle. It typically becomes evident by 40 to 45 years of age and it is expressed by a reduction in the ability to define letters or objects at near distance. The condition can be corrected by the use of single-vision or bifocal spectacles, PALs, or MF contact lenses.

[figure not shown]
Alcon manufactures three MF contact lenses (lotrafilcon B, nelfilcon A, and delefilcon A) with the same Precision Profile optical design that allows for the same fitting process with all three lenses. The AOHG MF soft contact lenses are made of a lens material that is approximately 33% water and 67% lotrafilcon B, a fluoro-silicone containing hydrogel which is surface-treated. These lenses may be prescribed for daily wear or extended wear for up to 6 nights of continuous wear with removal for disposal, or cleaning and disinfection prior to reinsertion, as recommended by the eye care professional.

The DACP MF daily disposable, soft contact lens is made up of 69% water and 31% nelfilcon A polymer (polyvinyl alcohol partially acetalized with N-formylmethyl acrylamide). DT1 MF (delefilcon A) daily disposable, soft contact lenses feature a unique water gradient composition from a silicone-rich highly breathable core (33% water) to an ultrasoft hydrophilic surface gel (> 80% water at the lens surface).

The goal of this study is to demonstrate seamless transition vision in presbyopes using Precision Profile Design MF contact lenses.

Page 27 of 59

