#### 7 INVESTIGATIONAL PLAN

## 7.1 Study Design

This is a prospective, randomized parallel group study measuring the average transition time

[figure not shown]
Habitual contact lens wearers will be randomized to either AOHG MF, DACP MF, or DT1 MF contact lenses. This will be a double-masked trial for the contact lens group. The PAL wearers will not be randomized and will wear their habitual PALs during the study. This group will not be masked. Investigators will be masked to the brand and type of PAL for habitual PAL wearers.

2.0; Most-Recent; Effective; CURRENT
Page 30 of 59

Subjects will be expected to attend 1 to 2 office visits (Visit 2 may be performed on the same day immediately following Visit 1). All study contact lenses will be prescribed according to the subject's prescription and fitted using the Alcon MF fitting guide. PAL wearers will wear their habitual spectacles. Subjects are expected to complete the study in approximately 2 to 3 hours.

The study is expected to be completed in approximately 8 weeks.

Figure 7-1 Study Design

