#### 8 STUDY POPULATION

The study population consists of male or female subjects aged  $\geq 38$  and  $\leq 58$  with presbyopia. The aim is to enroll approximately 60 subjects at approximately 2 sites; 1 in the United Kingdom and 1 in the United States (US), with a target of 48 total subjects completed. Each site is expected to enroll approximately 30 subjects with a target of 24 completed (approximately 6 subjects per group at each site). Site-specific targets may vary based upon individual site capabilities. Estimated time needed to recruit subjects for the study is approximately 6 to 8 weeks. Because a 20% screening failure and/or discontinuation rate is expected, approximately 60 subjects are expected to be enrolled.

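### The deciding MF-versus-PAL comparison is not randomised, yet its visible model contains only treatment; adjust for age and site and report it as non-randomised.

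*SAP*

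**What the plan says.** Both documents state the allocation openly. Protocol 7.1: "The PAL wearers will not be randomized and will wear their habitual PALs during the study". SAP 1.3: "Habitual PALs wearing subjects will not be randomized". Only habitual contact lens wearers are randomised, 1:1:1 among the three MF lenses. The design summary in SAP 1.2 still calls the study randomised and parallel-group, without a qualifier for the MF-PAL comparison.

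The SAP's decision criteria rest on that comparison: "Success of this study will be based on demonstration of noninferiority in transition time" for MF lenses against PALs, with a margin of 0.5.

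The model in SAP 4.3.1 is a mixed repeated-measures model "with a term for treatment (4 levels: AOHG MF, DT1 MF, DACP MF, and PAL"), and its pseudocode has "model transitiontime = lens". Protocol 12.4.1.2 names a generalized linear model, also with treatment as its only term. The one-sided 95% upper confidence limit (UCL) for pooled MF minus PAL decides noninferiority, and the same limit serves a further claim: "subsequent superiority will be tested and declared if UCL is less than 0".

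On balance between cohorts, Protocol 8 aims for "approximately 6 subjects per group at each site" but lets site targets vary. Protocol 8.1 sets one age range, 38 to 58 years, for everyone. No readable section matches or stratifies the two cohorts.

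**The concern.** Randomisation supports comparisons among the three MF lenses. It gives no protection to MF against PAL, because people choose spectacles or contact lenses for reasons that may also affect the outcome. The subject random effect and compound-symmetry structure in the SAP deal with repeated readings on one person, not with confounding.

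Age is a plausible confounder on the protocol's own background. Protocol 5.1 states: "Presbyopia is an age-related vision condition in which the crystalline lens gradually loses its ability to change shape", and says the condition becomes evident by 40 to 45 years. The entry range spans the years before and after that, and the endpoint is the time taken to shift between 4 m and 80 cm. Site matters because there are two sites in two countries, and the PAL-to-MF ratio at each is only a target.

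A bias favouring MF raises the chance of a false noninferiority claim and, by the same amount at the corresponding boundary, of a false superiority claim. A bias against MF costs power. Since neither size nor direction is known, the adjustment has to be chosen before the data are seen.

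**Working it through.** **Inputs.** Margin 0.5 s, one-sided α 0.05, common SD 0.456 s, 12 per group, and 24:8 for a 3:1 comparison (Protocol 12.8, SAP 7). Pooled MF against PAL at the planned completers is 36:12. I take 0.456 s as the between-subject SD of a subject's average time. The documents state no true difference for the power calculation; I assume 0.

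**The plan's own sample size.** With the noncentral t distribution, power is 79.9% at 11:11 and 83.1% at 12:12, and 78.9% at 21:7 and 83.6% at 24:8. So 12 per group and 24:8 are the smallest sizes that reach 80%, and the stated figures reproduce. Enrolment also agrees: 48/0.80 = 60.

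**Precision at 36:12.** SE = 0.456 × √(1/36 + 1/12) = 0.152 s. Four groups leave 48 − 4 = 44 df, with t = 1.680.

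**Effect of a confounding bias b (assumed range 0 to 0.20 s).**

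- Error when b favours MF = P(T₄₄ > 1.680), noncentrality b/0.152. This is the noninferiority error at a true difference of 0.5 s and the superiority error at a true difference of 0.
- Power when b is against MF and the true difference is 0 = P(T₄₄ > 1.680), noncentrality (0.5 − b)/0.152.

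| Bias b (s) | Error, bias favours MF | Power, bias against MF |
|---|---|---|
| 0 | 5.0% | 94.4% |
| 0.05 | 9.3% | 89.8% |
| 0.10 | 15.9% | 82.8% |
| 0.15 | 25.0% | 73.3% |
| 0.20 | 36.3% | 61.7% |

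Power stays at or above 80% up to a bias of 0.116 s.

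**What could produce such a bias.**

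- Age: bias = d × √R² × 0.456, where d is the cohort difference in age in SDs and R² is the share of outcome variance explained by age. With R² = 0.05 (assumed), d = 0.5 gives 0.5 × 0.224 × 0.456 = 0.051 s, and d = 1 gives 0.102 s.
- Site: zero if PAL wearers split 6:6. With PAL 8:4, MF 18:18 and an assumed site effect of 0.2 s, bias = (8/12 − 18/36) × 0.2 = 0.033 s, and the error is about 8%.

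**Cost of adjusting for age and site.** Two df are spent, and I assume no gain in residual variance. Power = P(T > t), noncentrality 0.5/(SE × √VIF), where VIF is the variance inflation from imbalance. One covariate differing by 1 SD at 3:1 gives VIF = 1 + (36 × 12)/48² = 1.1875. A 1 SD age gap together with the 8:4 site split gives about 1.21.

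| Completers | SE (s) | df, t | VIF 1 | VIF 1.19 | VIF 1.21 | 80% reached up to |
|---|---|---|---|---|---|---|
| 36:12 | 0.152 | 42, 1.682 | 94.4% | 90.7% | 90% | VIF 1.69 |
| 24:8 | 0.186 | 26, 1.706 | 83.4% | 77.5% | 77% | VIF 1.11 |

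**The case against.** The sponsor has fair replies.

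- **Redaction.** SAP 4.5, on subgroups and baseline factors, is listed in the contents but blacked out, as is much of what follows 4.3.1. An adjusted analysis may already exist. This stands as a limit on the claim: what can be said is that the visible decision rule does not use one.
- **Age and site are not shown to differ.** Both cohorts share the age limits and an ADD cap of +2.00 D, and the plan aims at site balance. Protocol 5.1 does not say that age affects this endpoint in corrected wearers. All true, so the magnitudes are illustrations. But shared limits narrow imbalance without ensuring balance.
- **The visible cohort differences lie elsewhere.** The 0.75 D cylinder limit (Protocol 8.1) and termination for an unsuccessful lens fit (Protocol 10) apply to contact lens wearers only. Age and site adjustment does not address these, or the choice of correction itself. This stands, and it is why the label is needed as well as the covariates.
- **Superiority is not the success criterion, and non-randomisation is disclosed.** Correct. Yet superiority is a prespecified claim read from the same UCL, and the success statement carries no qualifier.
- **Alternative models are allowed (SAP 4).** That clause gives non-convergence as its example and names no confounder. Choosing covariates after seeing the data is what prespecification should prevent.

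**Conclusion.** The concern holds, as an inexpensive improvement rather than a fatal flaw. The deciding comparison is non-randomised, and the visible model behind its UCL has treatment as its only fixed effect. The stated one-sided 5% error therefore applies to MF against PAL only if the two cohorts are exchangeable.

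Confidence in the practical size is moderate. It rests on an assumed bias, on 0.456 s being the between-subject SD, and on 36:12 completing. The sample size itself is not in error: at 36:12 it has room for two covariates.

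**What to change.** 1. In SAP 4.3.1 and Protocol 12.4.1.2, prespecify age (continuous) and site (two levels) as fixed covariates. Take the UCL for noninferiority and superiority from the adjusted MF-minus-PAL difference. In the pseudocode, add both to the MODEL statement and site to CLASS. If SAP 4.5 already holds such an analysis, carry it into 4.3.1.
2. Keep the unadjusted result as a sensitivity analysis.
3. Add sphere, cylinder or ADD only if a value from a common source, such as manifest refraction, is in the database for both cohorts. Habitual correction power is not comparable as recorded: it is contact lens power in one cohort and spectacle power in the other, and Protocol 8.1 states a vertex distance only for contact lens wearers.
4. Report the result, including any superiority statement, as a non-randomised comparison with residual confounding by habitual correction that adjustment cannot remove. Qualify the word randomised in SAP 1.2 accordingly.

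**Cost.** Age is collected (Protocol 10.2.1), and site follows from the listing of lens assignment by investigator (SAP 3), so no new data are needed. The work is a SAP revision and a change to Protocol 12.4.1.2, which falls under the amendment rules in Protocol 4. The statistical price is 2 df plus any variance inflation. That is affordable at 48 completers but could take power below 80% if completion fell to 24:8 with imbalanced cohorts.
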